9.0 DATA ANALYSIS/STATISTICAL METHODS

The statistical considerations summarized in this section describe the protocol-defined plan for data analysis of this study. A final and complete Statistical Analysis Plan (SAP) will be finalized prior to unblinding the data from the learning stage of the study (Part 1), possibly updated prior to unblinding the confirmatory stage of the study (Part 2). The SAP will supersede the protocol. Any deviations from the planned analyses will be described and justified in the final integrated study report.

This trial describes two studies (learning stage and confirming stage) with a common infrastructure in a single protocol. Statistical analysis of the clinical efficacy variables will be done for each of the study studies separately. Analysis of MRI volumetric data only applies to part 2 of the study. Statistical evaluation of adverse events will be done by each part separately and also integrated for the study as a whole. Statistical analysis of safety measures that are collected by visit will be done for the study as a whole (combined).

Continuous variables will be presented showing number of observations available, mean, median, minimum, maximum, 1st and 3rd quartiles, and standard deviations (or standard errors, depending on the variable) by visit. Categorical variables will be presented showing frequencies and percentages by visit.

All tests will be 2-sided and use an overall study-wise $\alpha = 0.05$ unless otherwise stated. SAS Version 9.4 or later will be used. Medical dictionary for Regulatory Activities (MedDRA) Version 21.0 or later will be used for coding adverse events. Medications will be coded using WHO Drug Dictionary (WHODD) Version March 2018 or later.

This study features a conditional sequential approach to hypothesis testing to control alpha, similar to methods using Bauer closed procedures.

9.1 POTENTIAL ADAPTIVE FEATURES

This study is planned to conform to regulatory guidance depicted in the FDA guidance *Adaptive Designs for Clinical Trials of Drugs and Biologics* (draft guidance, September 2018).

Part 1 of the study will inform the selection of a functional endpoint to serve as co-primary in Part 2, as well as the sample size required to adequately power the study to detect treatment effect on cognitive and functional measures in the study population.

Consistent with the FDA draft guidance on adaptive designs, it is acknowledged that interim analysis is common in trials, and it includes blinded analysis or unblinded analysis. In this study, however, Part 1 is intended to be completed, the database locked, and the analysis done as a final analysis, thereby avoiding the need for the interim analysis.

The planned features of the confirmatory phase (Part 2) that will be subject to modification informed by the learning phase (Part 1) of the study are:

- Primary endpoint(s) for Part 2
- Sample size for Part 2
- Study duration for Part 2
- Eligibility criteria for Part 2
- Dose of study drug for Part 2

9.2 SAMPLE SIZE DETERMINATION

Sample size considerations for Part 1:

Assuming a standard deviation of the change from Baseline to Month 6 in ADAS-cog14 of 4, using alpha = 0.05, a total sample size of approximately 82 subjects in balanced allocation (41 subjects per group) provides at least 90% power to detect a difference between treatment groups of 2.9 using a 2-sided, 2-sample t-test. Assuming a dropout rate of 18% or less, randomization of 100 subjects provides adequate statistical power for Part 1 to demonstrate superiority of azeliragon over placebo based on the ADAS-cog14.

Sample size considerations for Part 2:

Assuming a standard deviation of the change from Baseline to Month 18 in ADAS-cog14 of 7.5, using alpha = 0.049 (to include an adjustment for potential alpha inflation due to the independent data monitoring committee reviews), a total sample size of 120 subjects in balanced allocation (60 subjects per group) provides at least 90% power to detect a difference between treatment groups of 4.5 using a 2-sided, 2-sample t-test. Assuming a dropout rate of 25% or less, randomization of 160 subjects provides adequate statistical power for Part 2 to demonstrate superiority of azeliragon over placebo based on the ADAS-cog14.

9.3 RANDOMIZATION AND BLINDING**9.3.1 RANDOMIZATION**

This protocol includes two independent randomizations for the two stages of the adaptive study.

Subjects will be screened by Investigators or qualified designees to assess eligibility for randomization into the study. An interactive voice response system (IVRS)/interactive web response system (IWRS) will be used for assignment of treatment.

For each stage of the study, subjects will be enrolled and randomized according to a fixed randomization scheme blocked by study investigative site. There is no other stratification in the randomization scheme for either stage of the study.

Randomization will have balanced allocation (1:1) between azeliragon and placebo. Dropouts will not be replaced.

A randomization plan will be developed to guide the programming and security of the randomization scheme for this study.

9.3.2 BREAKING THE BLIND

The study will be double-blind. At the initiation of the study, the study site will be instructed on the electronic process for breaking the blind. Blinding should only be broken in emergency situations when knowledge of the treatment assignments is

necessary for subject safety. Upon breaking the blind, the reason must be documented in the electronic data capture system. The sponsor or representative should be consulted prior to breaking the blind except in emergency circumstances.

9.4 STATISTICAL HYPOTHESES

The learning stage has a single primary endpoint while the confirming stage of the study has two co-primary endpoints. The conditional sequence of hypothesis tests applies to both, acknowledging that the imaging endpoints will not exist for the learning stage of the study.

For each stage of this adaptive study, a 2-stage conditional sequence of statistical hypothesis tests will be used. The testing sequence will be as follows:

The first set of hypotheses to be tested is as follows:

- H_{01} : The mean change in ADAS-cog14 in the active group active group is equal to that of the placebo group.
- H_{11} : The mean change in ADAS-cog14 in the active group is not equal (is superior) to that of the placebo group.

Conditional on statistical significance, testing will proceed:

- H_{02} : The mean change in CDR-sb in the active group is equal to that of the placebo group.
- H_{12} : The mean change in CDR-sb in the active group is not equal (is superior) to that of the placebo group.

Conditional on statistical significance, testing will proceed:

- H_{03} : The mean change in FAQ in the active group is equal to that of the placebo group.
- H_{13} : The mean change in FAQ in the active group is not equal (is superior) to that of the placebo group.

Conditional on statistical significance within the confirmatory stage, testing will proceed:

- H_{02} : The mean change in MRI variable of analysis in the active group is equal to that of the placebo group.
- H_{12} : The mean change in MRI variable of analysis in the active group is not equal (is superior) to that of the placebo group.

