7.6 MRI

MRI scans will be performed at Screening in Part 1 and at Screening and Month 18 / Early Termination in Part 2. MRI scans will be read by a central reader prior to inclusion in the study to detect any exclusionary conditions such as stroke, hematoma, or intracranial tumor. The screening MRI should be performed at least 14 days prior to dosing to allow for the central read and interpretation of results prior to dosing. A local read is not required. Outside or prior MRI scans will not suffice for inclusion.

Specific MRI scan sequences required for safety and/or volumetric assessments will be outlined in the MRI procedures manual. Participants will be monitored, and images will be reacquired if there is subject movement during the scan. Volume,

surface area, and thickness values for all Freesurfer-generated regions will be assessed.

Brain magnetic resonance imaging (MRI) may include gadolinium contrast if the investigator determines that this is necessary for patient care either based on clinical signs or findings on the non-contrast MRI. Gadolinium may also be used when considered the standard operating procedure for the study site. Gadolinium should not be administered if the glomerular filtration rate <30 mL/min or equivalent creatinine clearance. However, this decision may be made by the PI on the basis of a change in the clinical status or may be done in response to a possible abnormality seen on the non-contrast brain MRI.

An MRI Imaging CRO will be responsible for standardizing the acquisition, training the MRI sites on the imaging protocol, ensuring equipment and image QA/QC and for overseeing a centralized read of the data. To ensure proper equipment and image QA/QC, the MRI Imaging CRO will have the MRI sites scan a phantom. Detailed procedures for obtaining and processing the MRI, conducting image QA/QC and endpoint analysis will be developed in study specific documents and provided as appropriate to the investigators, MR technicians, CRO personnel and endpoint readers.

Analysis of whole brain, ventricular, and hippocampal volumes will be conducted by a centralized reader(s) who will be blinded to subject treatment.

7.7

CT SCANS

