9.7 EFFICACY ANALYSIS

Efficacy evaluation will include the primary (ADAS-cog14 for Part 1) and co-primary endpoints (ADAS-cog14 and CDR-sb) for Part 2, key secondary measures, and other efficacy markers.

Statistical analysis will be done on each stage of the study, independently, for the primary / co- primary variables: change from baseline in ADAS-cog14 and change from baseline in CDR-sb. For all other secondary variables, and subgroup analyses, the study as a whole will be used for inferential purposes.

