9.7.1.2 Secondary Variables of Analysis

Part 1 secondary variables of analysis will include.

- Mean change from baseline in CDR-sb at Month 6.
- Mean change from baseline in the FAQ at Month 6.
- Mean change from baseline in the Amsterdam-IADL at Month 6.
- Mean change from baseline in eGFR at Month 6.

Part 2 will include the following secondary variables of analysis:

- Time to decline (to support responder analysis) where the specification of decline will be included in the SAP.

- Mean change from baseline in FAQ score at Month 18
- Mean change from baseline in Amsterdam-IADL score at Month 18
- Mean change from baseline in MMSE score at Month 18
- Mean change from baseline in eGFR at Month 18.
- Mean change from baseline in whole brain volume at Month 18.

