9.7.2 Statistical Methodology for Primary Analysis

The primary analysis will use the ITT methodology and a main-effects mixed-models for repeated measures (MMRM) methodology. The MMRM will utilize an unstructured covariance where the number of parameters is “ $t(t+1)/2$ ” where “ t ” is the dimension of the covariance matrix, using PROC MIXED in SAS. In the unlikely event of lack of convergence, Toeplitz structure will be employed where the number of parameters is “ t ” where “ t ” is the dimension of the covariance matrix. Time is considered as a class variable. Analysis will include treatment, time and treatment-by-time interaction as fixed effects, Baseline as covariate, and subject as a random effect. Supportive modeling will also include MMRM main-effects model with treatment, time, and subject.

Model assumptions will be evaluated. If the parametric assumptions are evaluated as inappropriate or violated, rank analogues will be advanced.

The primary analysis will be done for each stage separately. Part 1 will use alpha = 0.0499, which includes an adjustment of 0.0001 for interim analyses performed by the Independent Data Monitoring Committee (IDMC). The alpha adjustment for the IDMC for Part 1 is considered to be negligible, hence, the stated alpha for Part 1 is 0.05 for the 100-patient, 6-month trial. Part 2 will use alpha = 0.049, which includes an adjustment of 0.001 for interim analyses performed by the Independent Data Monitoring Committee (IDMC), thereby preserving the overall study-wise alpha = 0.05. The alpha adjustment of 0.001 is considered to be appropriate for the 200-patient, 18-month study.

Multiple imputations (MI) will be used as a supportive analysis with 100 invocations (acknowledging that more invocations are needed with more missing data). Monte Carlo methods are planned.

An essential component of the thorough analysis includes an assessment of the impact of missing data on study conclusions. As a part of assessing this impact, supportive analysis will include:

- an endpoint analysis (reduction to last-observation-carried-forward, justified in this study based on the monotonic progression of the natural course of AD and assuming no more dropouts in the group treated with azeliragon than in the group treated with placebo)
- a completers analysis (observed cases at endpoint)
- observed cases by assessment time.

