Interaction terms will be examined in supportive analyses. In the event of a significant interaction term, the impact on analysis conclusion will be examined. The primary model will not include interaction terms. A key supportive analysis will use the ITT methodology and a main-effects model for ANCOVA adjusting for baseline ADAS-cog14 (CDR-sb) using last-observation-carried-forward (LOCF) methods for missing data, justified based on known profiles of ADAS-cog14 (CDR-sb) in AD patients, which is conservative under the assumption that there are not more dropouts in the active-treated group than the placebo group. Rank ANCOVA will be done as a supportive analysis.

To ensure robustness of analysis conclusions against missingness, multiple imputation methods will also be done to cope with missing data as a key supportive analysis using the final on-treatment assessment of treatment failures as non-missing data at endpoint.

In accordance with the recommendations of the report from the National Academy of Science (NAS) panel *“The Prevention and Treatment of Missing Data in Clinical Trials,”* (National Research Council, 2010), missingness is classified as “missing at random” (MAR) or “missing not at random” (MNAR). When subjects are withdrawn due to treatment failure, this event is considered in this sensitivity analysis to be MNAR, and the endpoint value is taken as the hard endpoint (not imputed) in analysis, operationally, the endpoint analysis is the same as LOCF. Data that are missing for other reasons are considered to be MAR, and standard multiple imputation methods are planned.

Descriptive summaries will be produced of the observed values and change from Baseline in co-primary variables by treatment group at each individual time point and at endpoint (final on-treatment assessment for each subject).

For statistical analyses, 95% confidence intervals will be produced for the least-squares means (LSM) in each treatment group, as well as the LSM differences as compared to placebo. For MMRM and ANCOVA, two-sided p-values will be displayed for the comparison against placebo.

Because there are limited numbers of subjects per center, there will be inadequate power to explore impact of the center effect on study conclusion. Descriptive statistics by center will be presented.

The primary analysis controls alpha through the conditional sequence of hypothesis testing. No further adjustment for multiplicity is necessary.

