1.5 Study Design

TTP488-305 is a protocol that consists of two sequential, multi-center, randomized, double-blind, placebo-controlled, parallel group studies operationally conducted under a single protocol. The purpose of the study is to evaluate the safety and efficacy of 5 mg/day oral azeliragon relative to placebo in subjects with mild Alzheimer's disease (screening MMSE 21-26, baseline MMSE 19-27 and ADAS-cog14 score of ≥ 10) and impaired glucose tolerance (Screening HbA1c 6.5% - 9.5%, inclusive). Eligible participants will be randomly assigned to azeliragon or placebo in a 1:1 randomization for a double-blind dosing period of 6 months (Part 1) or 18 months (Part 2). The Part 1 and Part 2 studies will have independently randomized, unique study populations.

The Part 1, 6-month, double-blind treatment portion of the study will include 5 clinic visits. The primary objective of the Part 1 portion is to evaluate the efficacy of 6 months of oral azeliragon on a measure of cognition (ADAS-cog14). Secondary objectives of Part 1 will be to evaluate the efficacy of 6 months of oral azeliragon on multiple measures of function (CDR, Amsterdam-IADL, FAQ) to inform selection of a functional endpoint to serve as co-primary in Part 2. Additionally, Part 1 will be used to inform the sample size required to adequately power Part 2 of this study. The Schedule of Activities for Part 1 is described in Section 14 of this SAP.

Part 1 is conducted at multiple sites in the U.S and Canada.

The overall structure of the study includes the following periods:

Screening period: Screening procedures occur within 60 days of start of study drug administration, and they include obtaining informed consent and evaluations to determine eligibility for study participation.

Baseline Study Period: (Day -7 — Day 1, pre-dose): Subjects will have baseline assessments for efficacy and safety measures, including imaging and PK assessments.

Treatment Period: (Day 1 — Month 6): Subjects are treated with double-blind study medication. Efficacy and safety measures are taken. Blood samples are taken and subjects have assessments for safety and PK.

Follow-up period: (Month 9): Subjects return to the site for final safety assessments including vital signs, adverse events, electrocardiography and concomitant medications are taken. Blood draws are taken for safety evaluations and for pharmacokinetics evaluations.

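### Protocol 9.0 states a study-wise 5% for all tests, but the Part 2 sequence leaves four of six secondaries outside it and does not name its MRI variable

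*Protocol*

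**What the plan says.** Protocol 9.0 sets the general rule: "All tests will be 2-sided and use an overall study-wise" alpha of 0.05, unless otherwise stated. Protocol 9.7.2 gives the Part 2 final analysis 0.049 and reserves 0.001 for data monitoring committee looks, "thereby preserving the overall study-wise alpha = 0.05". The same section says that the primary analysis controls alpha through the conditional sequence and adds "No further adjustment for multiplicity is necessary". Section 9.7.5 repeats this for the primary efficacy analyses and requires no other adjustment.

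The sequence in 9.4 is ADAS-cog14, then CDR-sb, then FAQ, then, in Part 2 only, a step whose null hypothesis reads "The mean change in MRI variable of analysis in the active group is equal to that of the placebo group". That pair reuses the labels H02 and H12 already given to CDR-sb, and 9.4 names no MRI measure. Section 7.6 plans central analysis of three volumes: whole brain, ventricular and hippocampal.

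Section 2.2.2 lists six Part 2 secondaries: responder status at Months 6, 12 and 18, FAQ, Amsterdam-IADL, MMSE, eGFR and whole brain volume. Section 9.7.1.2 lists the same measures, for example "Mean change from baseline in Amsterdam-IADL score at Month 18", but replaces responder status with time to decline. Section 9.7.3 gives measurement secondaries methods similar to the primary analysis and responders a Cochran-Mantel-Haenszel test.

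SAP 1.5 says that Part 1 evaluates treatment "on multiple measures of function (CDR, Amsterdam-IADL, FAQ) to inform selection of a functional endpoint to serve as co-primary in Part 2". Protocol 9.1 makes the Part 2 primary endpoint open to change after Part 1.

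**The concern.** The general statement in 9.0 is wider than the procedure that is meant to support it. Four listed secondaries have test methods but no place in the sequence, no level of their own and no label as nominal or descriptive. A positive Part 2 result on Amsterdam-IADL, MMSE, eGFR or responder status could therefore be reported under a study-wise 5% statement that the plan does not deliver for it.

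Two gaps within the sequence add to this. The last step does not fix its variable, although three MRI volumes will be available. And Amsterdam-IADL, one of three candidates for the Part 2 functional co-primary, has no Part 2 hypothesis, while FAQ sits behind CDR-sb. If either were selected after Part 1, 9.4 as it stands would give it no place, or a gated one.

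**Working it through.** **1. The plan's own alpha.** Inputs are 0.049 for the Part 2 final analysis (9.7.2) and 0.0001 for each of at most 10 committee analyses (9.14). 0.049 + 10 × 0.0001 = 0.050. The stated figure reproduces.

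**2. The sequence itself.** Each step is tested only if the one before it succeeds. If all nulls are true, any rejection in the sequence needs a false rejection of ADAS-cog14, so the chance is at most 0.049. Provided each step names one variable, the bound also holds when some nulls are false, because an error needs rejection of the first true null at 0.049.

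**3. Coverage of the six Part 2 secondaries.**

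| Secondary (2.2.2) | In the 9.4 sequence? |
|---|---|
| FAQ | Yes, step 3 |
| Whole brain volume | Only if it is the MRI variable |
| Responder status, Months 6, 12, 18 | No |
| Amsterdam-IADL | No |
| MMSE | No |
| eGFR | No |

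Four are outside; it would be five if the MRI variable were hippocampal or ventricular volume.

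**4. Error across the sequence plus the outside tests.** Assumptions: all nulls true, each outside secondary read as a two-sided 0.05 test, and the sequence counted once at 0.049 through its ADAS-cog14 gate. Under independence with k outside tests, the chance of at least one false positive is 1 − 0.951 × 0.95^k.

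- Responder status counted once, k = 4: 1 − 0.951 × 0.8145 = 0.225.
- Responder status counted at three months, k = 6: 1 − 0.951 × 0.7351 = 0.301.

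The documents give no correlations, so a range is shown. It comes from simulation (2 million draws) of normal test statistics with a common correlation among the ADAS-cog14 gate, Amsterdam-IADL, MMSE and responder tests, and eGFR independent.

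| Common correlation | Responder once | Responder three times |
|---|---|---|
| 0 | 23% | 30% |
| 0.3 | 21% | 28% |
| 0.5 | 20% | 25% |
| 0.7 | 17% | 21% |
| 0.9 | 14% | 15% |

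If eGFR shared a correlation of 0.9 with the rest, the last row would fall to 10% and 11%.

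**5. The unnamed MRI step.** If the variable were picked after the data from three independent volumes at 0.049, the local error at that step would be 1 − 0.951³ = 0.140. The step is reached only after ADAS-cog14, CDR-sb and FAQ have all succeeded, so this adds nothing to the global-null figures in item 4.

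**The case against.** The strongest reply concerns scope. Sections 9.7.2 and 9.7.5 claim control only for the primary analyses, and 9.0 carries the qualifier that other statements may override it. A reader might infer that the Part 2 co-primary claim is inflated. The documents do not support that: ADAS-cog14 then CDR-sb in fixed order stays at 0.049. This part of the reply stands.

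A reader might also take "For all other secondary variables, and subgroup analyses, the study as a whole will be used for inferential purposes" in 9.7 as assigning the outside secondaries a nominal 5% level. In context that sentence contrasts the whole study with the separate stages; it says which data are used, not at what level. The 5% level in item 4 of the working is an assumption, and no single percentage is fixed by the documents. Counting responder status three times is also open to question, because 9.7.1.2 lists time to decline as a single item.

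On MRI, whole brain volume is the only volume listed as a secondary; the other two are exploratory in 2.2.2. It is very probably the intended variable, so a real 14% error is unlikely. That stands too, but 9.4 still does not say so.

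Finally, 9.0 lets the SAP supersede the protocol and be updated before Part 2 is unblinded, and changing the co-primary would call for revising 9.4 anyway. The SAP supplied covers Part 1 only, so its silence on Part 2 is not a defect. But the update is described only as possible, and that SAP's Part 1 sequence, which puts Amsterdam-IADL second (SAP 2), does not settle the Part 2 order. SAP 1.4 reports that Part 1 stopped at 43 subjects, which lowers the urgency without correcting the text.

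What remains is the mismatch between 9.0 and 9.4, the missing labels and the unnamed variable.

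**Conclusion.** The point holds as a matter of what Part 2 secondaries can claim. The primary and co-primary error rate is as stated. For four of the six Part 2 secondaries, the study-wise 0.05 in 9.0 has no procedure behind it. The size is conditional: about 14-23% with responder status counted once, or 15-30% counted at three months, for correlations of 0.9 down to 0 among the clinical endpoints with eGFR independent, all nulls true and each outside test read at 5%. The upper ends are the independence values; responder status and ADAS-cog14 come from the same scale, so the true figure is likely to be lower. The unnamed MRI variable and the missing place for a newly selected co-primary are gaps in specification, not shown errors.

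**What to change.** Make these changes in the protocol, or in a Part 2 SAP, before any Part 2 data exist:

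- In 9.4, name whole brain volume at Month 18 as the MRI step, and give that pair its own hypothesis number.
- In 9.4, define step 2 as the functional co-primary selected under 9.1, which is CDR-sb unless changed. A selected Amsterdam-IADL or FAQ then comes directly after ADAS-cog14. FAQ otherwise stays at step 3. If the selection changes, state where CDR-sb then goes.
- In 9.0, limit the study-wise 0.05 statement to the 9.4 sequence.
- Label Part 2 tests outside the sequence (Amsterdam-IADL unless selected, MMSE, eGFR, responder status, hippocampal and ventricular volume) as nominal, reported without significance claims.
- In 9.7.5, replace the 0.05 threshold with 0.049 for Part 2, to agree with 9.7.2.

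The cost is wording, plus the loss of confirmatory claims for secondaries outside the sequence. The sponsor could instead add some of them to the fixed order after the MRI step. That is a trade-off, because late entries can be claimed only if every earlier step succeeds, and the correction does not require it.
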